4.1 Description of study design

A total of 30 eligible patients will be enrolled. The enrolled patients will be randomized to one of 3 doses of pasireotide LAR (20 mg, 40 mg, or 60 mg) in a ratio of 1:1:1. Randomization will be stratified by prior medications (e.g. somatostatin analogues, dopamine agonists or GH receptor antagonists), (yes or no). Intramuscular administration of pasireotide LAR will be repeated every month (1 month = 28 days) for 12 months in core phase. It is permitted to increase the dose up to 60 mg in a patient showing the following biochemical test results after 3 and 6 months of study treatment: mean GH levels $\geq 2.5 \mu\text{g/L}$ and/or IGF-1 $> \text{ULN}$ (age and sex related). In the event of any problem with tolerability, it is permitted to reduce the next lower dosage level at any time. After 3 months of study treatment, the primary endpoint (proportion of patients with a reduction of mean GH levels to $< 2.5 \mu\text{g/L}$ and normalization of IGF-1 to within normal limits) will be evaluated.

Patients with a reduction of mean GH levels to $< 2.5 \mu\text{g/L}$ and normalization of IGF-1 at the end of the 12-month study treatment will be enrolled in an extension phase of study treatment. Patients with a mean GH level $\geq 2.5 \mu\text{g/L}$ and/or IGF-1 $> \text{ULN}$ at the end of the 12-month study treatment may be enrolled in an extension phase of study treatment if the extended study treatment is thought to be clinically beneficial for them by the investigator. Patients will receive pasireotide LAR in the extension phase until unacceptable toxicity appears or until the medication is commercially available or until the pasireotide LAR development program is discontinued whichever comes first.

Patients, who participate in the extension phase, will receive a 13th injection of the pasireotide LAR, the Visit 779 (Study completion) will be their last visit.

Figure 4-1 Study design

4.2 Timing of interim analyses and design adaptations

Not applicable

4.3 Definition of end of the study

Completion of the study as a whole (last patient last visit) will occur after all patients have completed all assessments as per [Table 7-1](#) and [Table 7-2](#) (core and extension phase) or have discontinued early.

4.4 Early study termination

The study can be terminated at any time for any reason by Novartis. Should this be necessary, the patient should be seen as soon as possible and the same assessments should be performed as described in [Section 7.1.3](#) for a prematurely withdrawn patient. The investigator may be informed of additional procedures to be followed in order to ensure that adequate consideration is given to the protection of the patient's interests. The investigator will be responsible for informing IRBs and/or ECs of the early termination of the trial.

5 Population

5.1 Patient population

The eligible patient population will consist of adult Japanese patients, with active acromegaly or pituitary gigantism.

The investigator or designee must ensure that only patients who meet all the following inclusion and none of the exclusion criteria are offered study treatment in the study.

5.2 Inclusion criteria

Patients eligible for inclusion in this study have to meet **all** of the following criteria:

1. Written informed consent obtained prior to any screening procedures
2. Male or female patients of at least 18 years of age
3. Patients with active acromegaly or pituitary gigantism following a or b
 - a. Patients with medication naïve acromegaly or pituitary gigantism demonstrated by:
 - a lack of suppression of GH nadir to <1 $\mu\text{g/L}$ after an oral tolerance test with 75 g of glucose (OGTT) (not applicable for diabetic patients) **or** a mean GH concentration of a 5-point profile within a 2 hour time period of > 5 $\mu\text{g/L}$
 - elevated circulating IGF-1 concentration (age and sex related)
 - Patients who have undergone one or more pituitary surgeries, but have not been treated medically or *de-novo* patients presenting a visible pituitary adenoma on MRI and who refuse pituitary surgery or for whom pituitary surgery is contraindicated

- b. Patients with inadequately controlled acromegaly or pituitary gigantism as defined by a mean GH concentration of a 5- point profile over a 2-hour period $> 2.5 \mu\text{g/L}$ and age and sex related IGF-1 $> 1.3 \times$ upper limit of laboratory normal (ULN), even if acromegaly have been treated for at least 12 weeks with somatostatin analogues or dopamine agonist
4. Patients with a known history or new diagnosis of impaired fasting glucose or diabetes mellitus may be included, however blood glucose and antidiabetic treatment must be monitored closely throughout the trial and adjusted as necessary (see [Section 6.3.3](#))

5.3 Exclusion criteria

Patients eligible for this study must not meet **any** of the following criteria:

1. For patients with inadequately controlled acromegaly or pituitary gigantism with current medication.
 - Patients who have been treated with dopamine agonists during the last 8 weeks prior to visit 1 (screening).
 - Patients who have been treated with long -acting somatostatine analogues during the last 4 weeks prior to visit 1 (screening).
 - Patients who have been treated with GH receptor antagonists during the last 8 weeks prior to visit 1 (screening). Such patients must have been treated with long -acting somatostatine analogues or dopamine agonists monotherapy continuously for a minimum of 12 weeks prior to starting GH receptor antagonists therapy and they should have been inadequately controlled on monotherapy.
2. Patients who have received pasireotide (SOM 230) prior to enrollment
3. Patients with compression of the optic chiasm causing any visual field defect for whom surgical intervention is indicated.
4. Patients who require a surgical intervention for relief of any sign or symptom associated with tumor compression
5. Patients who have undergone major surgery/surgical therapy for any cause within 4 weeks of visit 1
6. Patients who have received radiotherapy (except for pituitary irradiation) for any reason in the 4 weeks prior to visit 1 must have recovered from any side effect of radiotherapy
7. Patients who have received pituitary irradiation within the last three years prior to visit 1
8. Patients who are hypothyroid and not adequately treated with stable doses of thyroid hormone replacement therapy
9. Diabetic patients whose blood glucose is poorly controlled as evidenced by HbA1c $>8\%$
10. Patients with symptomatic cholelithiasis
11. Patients with abnormal coagulation (PT and/or APTT elevated by 30% above normal limits) or patients receiving anticoagulants that affect PT (prothrombin time) or APTT (activated partial thromboplastin time)
12. Patients who have congestive heart failure (NYHA Class III or IV), unstable angina, sustained ventricular tachycardia, ventricular fibrillation, clinically significant bradycardia, advanced heart block or a history of acute myocardial infarction within the six months preceding enrollment

13. Patients with risk factors for torsade de pointes, i.e. patients with a baseline QTcF > 470 ms, hypokalemia, hypomagnesemia, hypocalcemia, family history of long QT syndrome, or patients receiving a concomitant medication known to prolong QT interval.
14. Patients with confirmed central hypothyroidism, central hypoadrenalism and diabetes insipidus, unless they are adequately treated with stable doses of hormone replacement therapy for a minimum of three months prior to study entry (first dose of study medication). Patients with confirmed central hypogonadism unless they are adequately treated with stable doses of hormone replacement therapy for a minimum of three months prior to study entry (first dose of study medication) except in cases where hormones replacement therapy is not indicated.
15. Patients with history of liver disease such as cirrhosis, chronic active hepatitis B or C, or patients with ALT or AST more than 2 x ULN, baseline total bilirubin > 1.5 x ULN
16. Presence of Hepatitis B surface antigen (HbsAg)
17. Presence of Hepatitis C antibody (anti-HCV)
18. Patients with WBC <3 x 10⁹/L; Hgb < 90 % LLN; PLT <100 x 10⁹/L
19. Patients who have any current or prior medical condition that may interfere with the conduct of the study or the evaluation of its results in the opinion of the Investigator
20. Female patients who are pregnant or lactating, or are of childbearing potential (defined as all women physiologically capable of becoming pregnant) and not practicing an effective method of contraception/birth control. Female patients of child bearing potential and sexually active males must use a condom during intercourse while taking the drug and for 3 months after the last dose of study drug and should not father a child in this period. A condom is required to be used also by vasectomized men in order to prevent delivery of the drug via seminal fluid. Effective contraception methods include:
 - Use of oral, injected or implanted hormonal methods of contraception
 - Placement of an intrauterine device or intrauterine system
 - Barrier methods of contraception: condom or occlusive cap (diaphragm or cervical/vault caps) with spermicidal foam/gel/film/cream/ vaginal suppository
 - Total abstinence
 - Patient sterilization (male or female)
21. Patients who have a history of alcohol or drug abuse in the 12 month period prior to receiving pasireotide LAR
22. Patients who have given a blood donation (of 400 ml or more) within 2 months before receiving pasireotide LAR
23. Patients who have participated in any clinical investigation with an investigational drug within 1 month before receiving pasireotide LAR
24. Known hypersensitivity to somatostatin analogues or any components of the LAR formulation
25. Patients with active malignant disease within the last five years (with the exception of basal cell carcinoma or carcinoma in situ of the cervix)
26. Patients with the presence of active or suspected acute or chronic uncontrolled infection

27. Patients with a history of non-compliance to medical regimens or who are considered potentially unreliable or will be unable to complete the entire study
28. Known gallbladder or bile duct disease, acute or chronic pancreatitis

6 Study treatment

6.1 Study treatment

Investigational study treatment: pasireotide LAR i.m.

6.1.1 Dosing regimen

Patient will receive one of three pasireotide LAR i.m. doses of 20, 40, or 60 mg. Intramuscular administration of pasireotide LAR will be repeated every month (1 month = 28 days) for 12 months in core phase. It is permitted to increase the dose up to 60 mg in a patient showing the following biochemical test results after 3 and 6 months of study treatment: mean GH levels ≥ 2.5 $\mu\text{g/L}$ and/or IGF-1 > ULN (age and sex related). In the event of any problem with tolerability, it is permitted to reduce next lower dosage level at any time.

6.1.2 Ancillary treatments

Not applicable.

6.1.3 Rescue medication

Not applicable.

6.1.4 Guidelines for continuation of treatment

Patients may continue treatment provided no tolerability issues are present (See [Section 6.3](#)) and criteria for discontinuation are not met (see [Section 7.1.3](#)).

6.1.5 Treatment duration

Patients will be treated for 12 months in the core phase of the study and will have the option to continue study treatment for 12 more months in the extension phase of the study.

6.2 Dose escalation guidelines

Not applicable.

6.3 Dose modifications

6.3.1 Dose modification and dose delay

Dose up-titration

Dose increases is permitted after the first three months of treatment (steady-state reached) if biochemical parameters show a mean GH level ≥ 2.5 $\mu\text{g/L}$ and/or IGF-1 $>$ ULN (age and sex related) and there are no tolerability issues (see [Table 6-1](#)). Patients on the 20 mg arm with a mean GH level ≥ 2.5 $\mu\text{g/L}$ and/or IGF-1 $>$ ULN (age and sex related) after the Month 2.75 (Visit 11) GH and IGF-1 assessment will have their dose increased to 40 mg at Month 3 (Visit 12), if there are no tolerability issues. Patients on the 40 mg arm with a mean GH level ≥ 2.5 $\mu\text{g/L}$ and/or IGF-1 $>$ ULN (age and sex related) after the Month 2.75 (Visit 11) GH and IGF-1 assessment will have their dose increased to 60 mg at Month 3 (Visit 12), if there are no tolerability issues. At Month 7 (Visit 16), patients receiving 20 mg and 40 mg doses with mean GH level ≥ 2.5 $\mu\text{g/L}$ and/or IGF-1 $>$ ULN (age and sex related) after the Month 6 (Visit 15) GH and IGF-1 assessment will have their dose increased to 40 mg and 60 mg, respectively, if there are no tolerability issues. Patients receiving the 60 mg dose at Month 3, 6 or 9 with a mean GH level ≥ 2.5 $\mu\text{g/L}$ and IGF-1 $>$ ULN (age and sex related) will be discontinued from the study unless clinical benefit has been observed as per the investigator's judgment.

Patients that have a mean GH level < 2.5 $\mu\text{g/L}$ and IGF-1 \leq ULN (age and sex related) on current therapy after Month 3 and/or Month 6 will be kept on their current dose.

After Month 12, the timing of the dose adjustments will be based on GH and IGF-1 values, at the investigators discretion but must include duration of at least 3 months on a current dose prior to up-titration and no tolerability issues are present. Patients receiving the 60 mg dose after Month 12 with a mean GH level ≥ 2.5 $\mu\text{g/L}$ and IGF-1 $>$ ULN (age and sex related) will be discontinued from the study unless clinical benefit has been observed as per the investigator's judgment.

Dose down-titration

Dose reduction is due to lack of tolerability (refer to [Table 6-2](#) and [Table 6-3](#)) will be allowed as one dose level reduction at a time (i.e. from 60 mg to 40 mg or from 40 mg to 20 mg) If tolerability issue is resolved, increase dose to that prior to the dose reduction unless investigator opinion to remain on current dose.

These changes must be recorded on the Dosage Administration Record CRF.

Dose interruption

If a patients requires a dose interruption of >28 days from the intended day of the next scheduled dose (>56 days from the previous dose), then the patient must be discontinued from the study.

Table 6-1 Dose titration steps for pasireotide LAR

| | Dose level 0 | Dose level 1 | Dose level 2 |
|-----------------------|--------------|-----------------------------|-----------------------------|
| Dose increase | | | |
| SOM230 LAR | 60 mg | Not applicable ¹ | Not applicable ¹ |
| SOM230 LAR | 40 mg | 60 mg | Not applicable ¹ |
| SOM230 LAR | 20 mg | 40 mg | 60 mg |
| Dose reduction | | | |
| SOM230 LAR | 60 mg | 40 mg | 20 mg |
| SOM230 LAR | 40 mg | 20 mg | Not applicable ² |
| SOM230 LAR | 20 mg | Not applicable ² | Not applicable ² |

¹ Dose increase above 60 mg is prohibited.

² Dose reduction below 20mg is prohibited. Dose reduction should be based on the worst toxicity demonstrated at the last dose.

Table 6-2 Guideline for treatment of patients experiencing adverse events

| Adverse event | Action |
|---|---|
| AE CTC grade ≤ 2 | No drug adjustments |
| AE CTC grade ≥ 3 and assessed as study drug related | Reduce pasireotide LAR i.m. dose from 60 mg to 40mg 40 mg to 20mg 20 mg - discontinue If AE improves to grade ≤ 2 before the next administration, increase dose to that prior to the dose reduction unless investigator opinion is to remain on current dose. If the dose is increased and the AE recurs at CTC grade ≥ 3, the dose should be reduced again and the patient should stay on this lower dose and no further dose titrations are allowed. If AE does not improve to grade ≤ 2 on the minimum dose the patient will be withdrawn. |

For the management of QT prolongation and LFT increases refer to specific instructions provided in Special Safety in [Section 6.3.3 \(Figure 6-2 and Figure 6-3\)](#).

Table 6-3 Guideline for treatment of patients experiencing adverse events in QTcF

| Adverse event | Action |
|--|--|
| CTC grade 1 (QTcF ≤ 470 msec) | No study drug adjustments |
| CTC grade 2 (470 < QTcF ≤ 500 msec) | No study drug adjustments Patient is to be referred to a cardiologist for evaluation and appropriate management. Patient can remain in the study (unless discontinuation is recommended by cardiologist) |
| CTC grade ≥ 3 (QTcF > 500 msec) | Dose is interrupted until a cardiologist consult obtained. If QTcF >500 is confirmed by cardiologist, the patient is to be discontinue |

See Section 6.3.3 for further guidance on QTcF adverse events

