As outlined in [Table 6-2](#), patients with grade 3 hyperglycemia (FPG value >250 mg/dL; >13.9 mmol/L) at any point in the study should have the dose of pasireotide decreased. Patients who in spite of appropriate therapeutic interventions and despite dose reduction of study drug develop uncontrolled diabetes mellitus and/or consistently high blood glucose values: FPG ≥ 240 mg/dL (13.3 mmol/L) or HbA1c value ≥ 10 % will require study treatment discontinuation as outlined in [Section 7.1.3.1](#).

Figure 6-1 Fasting self-monitoring blood glucose guidelines

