7.1.3.1 Criteria for premature patient withdrawal

Patients may voluntarily withdraw from the study or be dropped from it at the discretion of the investigator at any time. Patients may be withdrawn from the study if any of the following occur:

- Adverse event(s) [including abnormal laboratory value(s) and abnormal test procedure result(s)]
- Protocol deviation (including but not limited to, new therapy for acromegaly, and discovery of patient ineligibility)
- Patient withdrew consent

- Lost to follow-up
- Administrative problems
- Death
- Disease progression
- Pregnancy
- Treatment duration completed as per protocol

The investigator must also inform the premature withdrawal to Novartis, if this occurs during the core period.

In addition to the general withdrawal criteria, the following **study specific criteria** will also require study treatment discontinuation:

- Patients experiencing unacceptable toxicity, as described in [Table 6-2](#), [Table 6-3](#).
- Patients unable to tolerate the lowest dose (20 mg) as per [Section 6.3](#).
- Patients with > 28 consecutive days of treatment interruption (either due to tolerability, investigator decision or patient compliance)
- Uncontrolled diabetes mellitus, consistently high glucose values FPG \geq 240 mg/dL (13.3 mmol/L) or HbA1c value \geq 10 % despite prior appropriate management and prior dose adjustment of the study drug,
- Patients experiencing adverse events in QTc:
 - a confirmed QTcF $>$ 470msec and discontinuation recommended by a cardiologist, or
 - Mean QTcF $>$ 500 msec measured by triplicate ECGs
 - Significant arrhythmia findings from Holter monitoring such as:
 1. Any ventricular or supra-ventricular tachyarrhythmia associated with symptoms of hemodynamic compromise
 2. Sustained ventricular tachycardia ($>$ 30 sec) irrespective of symptoms
 3. Recurrent non-sustained ventricular tachycardia (\geq 3 beats) during any 24-hour monitoring period
 4. Torsades de Pointes
 5. Cardiac arrest
 6. Pause $>$ 5 seconds
 7. Second or third degree AV block
 - New occurrence of clinically significant/symptomatic bradycardia, or
 - Increased risk of QT prolongation by use of QT prolonging medication, or
 - Hypokalemia ($<$ 3.5 mmol/L) or hypomagnesaemia ($<$ 0.7 mmol/L) confirmed by repeat testing that is either a new finding or accompanied by vomiting or diarrhea and not corrected by treatment.
- Patients experiencing the abnormal hepatic criteria below:

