7.2.2.6 Tolerability

In addition to general safety data, information on dose reductions will be collected.

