4. Action taken with respect to study or investigational treatment (none, dose adjusted, temporarily interrupted, permanently discontinued)
5. Whether medication or therapy taken (no concomitant medication/non-drug therapy, concomitant medication/non-drug therapy)
6. Whether it is serious, where a serious adverse event (SAE) is defined as in [Section 8.2.1](#)

All adverse events should be treated appropriately. If a concomitant medication or non-drug therapy is given, this action should be recorded on the Adverse Event eCRF. However the elevation of GH, IGF-1 and PRL values should not be reported as an adverse event.

Once an adverse event is detected, it should be followed until its resolution or until it is judged to be permanent, and assessment should be made at each visit (or more frequently, if necessary) of any changes in severity, the suspected relationship to the study treatment, the interventions required to treat it, and the outcome.

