10.5.3.5 Tolerability

Tolerability will be studied in terms of dose reductions or drug interruption due to an AE.

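### The tolerability measure omits permanent discontinuation due to an AE, so read alone to Month 3 it can flatter the 20 mg starting dose; separately, the instructions for a grade ≥ 3 AE on 20 mg do not agree

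*Protocol*

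**What the plan says.** **How tolerability is measured.** Protocol Section 10.5.3.5: "Tolerability will be studied in terms of dose reductions or drug interruption due to an AE". Section 7.2.2.6 is narrower still: "In addition to general safety data, information on dose reductions will be collected". Section 10.5.3.1 presents safety tables by dose level up to Month 3 and for all patients combined afterwards. SAP Section 5.7 counts patients with a dose reduction or a dose increase, by study phase.

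**Where the measure sits.** In Table 3-1, tolerability and safety at 3 months is a key secondary objective. Its endpoint is CTC-graded toxicity together with laboratory and special safety assessments. Dose changes are not named there.

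**What can happen to a 20 mg starter.** Up-titration first becomes possible at Month 3 (Section 6.3.1). A footnote to Table 6-1 adds: "Dose reduction below 20mg is prohibited".

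**Instructions for a drug-related grade ≥ 3 AE.** The steps in Table 6-2 end with "40 mg to 20mg 20 mg - discontinue". The last sentence of the same cell reads "If AE does not improve to grade ≤ 2 on the minimum dose the patient will be withdrawn". Section 6.3.3.1 cites Table 6-2 and says that patients with grade 3 hyperglycaemia "at any point in the study should have the dose of pasireotide decreased". Section 7.1.3.1 lists "Patients unable to tolerate the lowest dose (20 mg) as per" Section 6.3 among the reasons to stop, which only sends the reader back.

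**What is recorded.** For each AE, Section 8.1.1 collects: "Action taken with respect to study or investigational treatment (none, dose adjusted, temporarily interrupted, permanently discontinued". Interruption and permanent discontinuation are separate categories. SAP Section 5.10.1 plans a table of AEs leading to study discontinuation, by phase, and a listing of AEs leading to study drug discontinuation. SAP Section 5.3 summarises discontinuation reasons.

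**The concern.** The three starting doses do not have the same outcomes open to them. At 40 and 60 mg a drug-related grade ≥ 3 AE leads to a lower dose, which the measure counts. At 20 mg there is no lower dose, and the action named first in Table 6-2 is one that the measure does not count. A by-dose summary of the measure to Month 3 therefore has a lower ceiling for 20 mg, whatever the true tolerability. A reader choosing among starting doses could take a low 20 mg figure as evidence about the drug when part of it comes from the definition.

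The second issue is that a site facing such an AE on 20 mg finds instructions that do not clearly agree. Sites may act differently, and what they do determines which category the patient enters.

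**Working it through.** The plan states no figure for this point, and the sample-size calculation does not bear on it. The check sets the rules side by side and then scales the effect.

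**Step 1. How one event is counted.** Take a drug-related grade ≥ 3 AE in Months 0–3, handled under Table 6-2, with no dose interrupted.

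| | 40 or 60 mg, reduced | 20 mg, stopped | 20 mg, no change |
|---|---|---|---|
| Reduction | 1 | 0 | 0 |
| Interruption | 0 | 0 | 0 |
| Measure in 10.5.3.5 | 1 | 0 | 0 |
| Measure plus discontinuation due to an AE | 1 | 1 | 0 |

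The zero for reductions at 20 mg holds under any reading of Table 6-2. It follows from the floor in Table 6-1 and from the first up-titration being at Month 3. The gap in the measure is therefore independent of the inconsistency checked in Step 3.

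**Step 2. Size.** Inputs: 1:1:1 allocation (Protocol Section 4.1), 30 planned and 33 randomised (SAP Section 2), so 30/3 = 10 or 33/3 = 11 per arm. The documents give no rate of drug-related grade ≥ 3 AEs by dose, so the rate q over Months 0–3 is an assumption. Further assumptions: the same q in each arm, every 40 and 60 mg case reduced, every 20 mg case stopped without a prior interruption. The expected count on the current measure is then n × q at 40 mg, n × q at 60 mg and 0 at 20 mg. With discontinuation added it is n × q in all three. The chance of at least one uncounted 20 mg patient is 1 − (1 − q)^n.

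| q | n = 10: expected uncounted | n = 10: chance of ≥ 1 | n = 11: expected uncounted | n = 11: chance of ≥ 1 |
|---|---|---|---|---|
| 5% | 0.5 | 40% | 0.55 | 43% |
| 10% | 1.0 | 65% | 1.1 | 69% |
| 20% | 2.0 | 89% | 2.2 | 91% |

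For scale, the exact 95% interval is 0% to 28.5% for 0/11 and 2.3% to 51.8% for 2/11. The distortion is in a descriptive figure whose uncertainty is already wide.

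**Step 3. The instructions at 20 mg.**

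| Source | AE improves to grade ≤ 2 | AE does not improve |
|---|---|---|
| Table 6-2, step list | discontinue | discontinue |
| Table 6-2, last sentence | withdrawal not called for | withdraw |
| Section 6.3.3.1, grade 3 hyperglycaemia | decrease dose | decrease dose |
| Table 6-1, footnote | decrease not allowed | decrease not allowed |

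Within Table 6-2, the two lines agree when the AE persists and differ, by implication, when it improves. For grade 3 hyperglycaemia the mismatch is direct: Section 6.3.3.1 calls for a decrease with no exception at 20 mg, while Table 6-1 rules one out and Table 6-2 says to discontinue.

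**The case against.** The case against is substantial, and most of it limits the point.

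- **The measure is a supplement.** Table 3-1 defines the key secondary endpoint as graded toxicity, and Section 7.2.2.6 introduces dose reductions as an addition to general safety data. This stands.
- **The event is recorded elsewhere.** A reader might infer that intolerance at 20 mg goes unseen. The documents do not support that. The AE page has a category for permanent discontinuation, AEs are summarised by grade and relation to treatment (Section 10.5.3.2) and by dose to Month 3 (Section 10.5.3.1), and the SAP tabulates and lists AEs leading to discontinuation. What remains is that the SAP table is by phase, not by starting dose.
- **Some 20 mg patients are counted.** The QTcF rule (Table 6-3) and the liver rule (Section 6.3.3.3) can interrupt a dose first, and an interruption due to an AE enters the measure. This stands.
- **Table 6-2 may be consistent with itself.** A reader might infer that it both stops and keeps the same patient. No sentence says that a patient is kept, and the last sentence can be read as covering patients already reduced to 20 mg. Nothing in the cell confirms that reading, however, and it does not resolve the conflict with Section 6.3.3.1.
- **A rate should not be borrowed from the phase III study.** Adding its grade 3 or 4 hyperglycaemia (2.8%) and diabetes mellitus (5.6%) gives 8.4%, or 0.084 × 11 = 0.92 patients, and suggests about one per arm. Those rates come from a 40 mg start over 12 months, may overlap and are not limited to drug-related events. With uniform onset assumed, 0.92 × 3/12 = 0.23. The Japanese healthy-volunteer data also show fewer events at 20 mg (blood glucose increased in 3/8, against 8/8 at 40 mg and 6/8 at 60 mg). Fewer than one patient is plausible, and some true advantage for 20 mg is possible.
- **No test between doses is planned.** The comparison is descriptive, so there is no error rate to distort. This stands.
- **The relevant plan is not supplied.** SAP Section 5.10 says that analyses through Month 3 were reported in the 12-month CSR. Whether that report shows discontinuations due to AEs by starting dose cannot be checked here.

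**Conclusion.** The point holds in a limited form. As defined in Section 10.5.3.5, the tolerability measure is structurally lower for 20 mg in the by-dose comparison to Month 3. Reductions there are impossible, and a patient stopped for an AE without a prior interruption is not counted. Read on its own, the measure can make 20 mg look better tolerated; read beside the graded AE summaries by dose, much of that impression can be corrected. At an assumed q of 5% to 20%, about 0.5 to 2 of 10 or 11 patients would be uncounted, given equal rates across arms and the stopping line applied. The documents fix no value of q.

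A reader might go further and infer an efficacy bias, since a patient stopped before Month 3 counts as a non-responder. One patient is up to 1/11 = 9.1 points in the 20 mg arm and 1/33 = 3.0 points overall, but only if that patient would otherwise have responded. The non-responder rule is pre-specified for all arms, and the sample size allows for 10% dropout. The documents do not support more than this upper bound.

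Separately, Table 6-2, Table 6-1 and Section 6.3.3.1 do not agree on a drug-related grade ≥ 3 AE arising on 20 mg and need reconciling. Which rule is right is a clinical decision outside this review.

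**What to change.** 1. In Section 10.5.3.5 and in the analysis plan that covers Month 3, report by starting dose the proportion of patients with a dose reduction, an interruption or permanent discontinuation due to an AE, with the three components shown separately. The action-taken field in Section 8.1.1 supplies the data. First check whether the 12-month CSR already shows this. If it does not, a supplementary table in the final CSR would serve, labelled as added after the Month 3 results.
2. Read that table beside drug-related grade ≥ 3 AEs by starting dose. The combined measure still misses a 20 mg patient who has such an AE and continues unchanged, as the last column of the Step 1 table shows.
3. The sponsor's clinicians should reconcile the step list and last sentence of Table 6-2, the floor in Table 6-1, and Section 6.3.3.1, so that one action is stated for a drug-related grade ≥ 3 AE arising on 20 mg. Section 7.1.3.1 should then point to it.

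The cost is one extra summary row (with its components) and a wording change in the dose-modification text. No new data are needed. The 20 mg tolerability figure may look less favourable.
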